Inflammation and Thrombosis in Patients With Severe Aortic Stenosis After
Transcatheter Aortic Valve Replacement (TAVR)

NCT02486367

January 31, 2019

Supplementary Clinical Study Protocol

Title: Platelet and Monocyte Activation After Transcatheter Aortic Valve Replacement (POTENT-TAVR)

Subtitle: POTENT-TAVR: A Mechanistic Randomized Trial of Ticagrelor versus Clopidogrel

Table of Contents

1. Cover page	2
2. Synopsis.....	3
3. Introductory Background.....	4
4. Study objectives.....	6
5. Study design.....	7
6. References.....	12

1. Cover page

Title: Platelet and Monocyte Activation After Transcatheter Aortic Valve Replacement (POTENT-TAVR): POTENT-TAVR: A Mechanistic Randomized Trial of Ticagrelor versus Clopidogrel

Acronym: POTENT_TAVR

Test drug: Ticagrelor

Active Control: Clopidogrel

Clinical study phase: Phase 4

Sponsor: AstraZeneca

Principal Investigator:

[name]

Associate Professor of Medicine

Case Western Reserve School of Medicine

[name]

[contact]

Compliance Statement:

The study will be conducted in compliance with the protocol and any applicable regulatory requirements.

Confidentiality

The information provided in this document is strictly confidential and is intended solely for the guidance of clinical investigation. Reproduction or disclosure of this document - whether in part or in full - to parties not associated with the clinical investigation, or its use for any other purpose, without the prior written consent is not permitted.

2. Synopsis

Title: Platelet and Monocyte Activation After Transcatheter Aortic Valve Replacement (POTENT-TAVR)

Clinical study phase: Phase 4

Study objective(s): 1. To determine whether high-potency ADP receptor blockade reduces measures of platelet activation in patients after TAVR. 2. To determine whether high-potency ADP receptor blockade mitigates the pro-thrombotic inflammatory response observed after TAVR.

Test drug: Ticagrelor

Dose: 90mg twice daily

Route of administration: Oral

Duration of treatment: The first dose of Ticagrelor will be started (180mg load) the morning of planned TAVR. Treatment will continue for 30 days.

Active Comparator: Clopidogrel

Dose: 75 mg once daily

Route of administration: Oral

Duration of treatment: The first dose of Clopidogrel will be given (300 mg load if P2Y12 naïve or 75mg if P2Y12 non-naïve) the morning of planned TAVR. Treatment will continue for 30 days.

Background treatment: Cardiovascular medications will be continued without planned dose titration as per standard after TAVR. Low dose aspirin 81mg once daily will be initiated on the day of TAVR or continued as pre-existing therapy.

Indication: Aortic Stenosis and planned transcatheter aortic valve replacement (TAVR).

Primary Endpoints: P2Y12 platelet responsiveness (PRU) using the VerifyNow assay at 1 day post procedure and the percentage of inflammatory (CD14+CD16+) monocytes (compared to total monocytes) 1 day after TAVR.

Key inclusion criteria: 1) Valvular heart disease and a clinical indication for TAVR, 2) Age of 18 years or older, 3) Capable of informed consent. 4) Planned transfemoral TAVR.

Key exclusion criteria: 1) Prior history of stroke, transient ischemic attack (TIA), or intracranial hemorrhage, 2) Established bleeding diathesis or thrombocytopenia (<150k/dl), 3) End-stage renal disease, 4) Severe hepatic impairment or liver cirrhosis, 5) Pregnancy, 6) Current infection, 7) History of autoimmune disease, 8) Established allergy to contrast agents, thienopyridines, aspirin, or ticagrelor, 9) History of solid organ transplantation, 10) Atrial Fibrillation, DVT, PE or other indication for long term anti-coagulation, 11) Plan for direct aortic access or trans-apical TAVR, 12) Enrollment in another clinical trial, 13) Recent (< 12 months) or active excessive bleeding.

Type of control: Active treatment

Clinical Event Committee: No

Data Safety Monitoring Board Yes

Number of subjects: A total of 60 subjects will be randomized.

3. Introductory Background

Transcatheter Aortic Valve Replacement (TAVR) has emerged as an important alternative to surgical aortic valve replacement. While this technology represents an important advance over medical therapy or surgical AVR in poor operative candidates, the absolute mortality rates remain high, even in the great majority in whom an optimal hemodynamic result is achieved. In the randomized literature, the majority of these patients die within two years and two thirds of these deaths are due to cardiovascular (CV) events¹.

The mechanisms responsible for this limited survival are unclear from the clinical trials completed to date. While persistent valve disease undoubtedly plays a role in a subset of patients, particularly in patients with significant aortic regurgitation, the majority of events are due to non-valve related co-morbidities.

Our multi-disciplinary group includes members with broad expertise in cardiovascular and immunologic clinical research. The over-arching aim of our collaborative work to date is to identify shared mechanisms of inflammation and thrombosis that correlate with cardiovascular disease. Recent work from our group has focused on the prothrombotic phenotype of activated inflammatory monocytes which are preferentially expanded in both HIV and ACS².

Clopidogrel treated patients following TAVR have a 64.3% rate of platelet hyporesponsiveness (VerifyNow assay, hyporesponsiveness defined as PRU <208)³. In this post-TAVR population (n=28) the median PRU was 244.5 (interquartile range 164.8-290.3). In preliminary experiments, we find a profile of immune activation after TAVR characterized by the expansion of CD14+CD16+ inflammatory monocytes, a marker we and others have found correlates with adverse cardiovascular events^{2,4}. Of note, we have previously demonstrated that inflammatory monocytes express high levels of tissue factor and this feature also correlates with ACS². Thus, post-TAVR patients represent a patient population in which high-potency ADP receptor blockade may provide protection against MACE.

[figure not shown]

Figure 1. Mechanistic hypothesis of TAVR leading to platelet activation and inflammation

Hypothesis

Our hypothesis is that TAVR results in at least three simultaneous CV insults: 1) the abrupt release of severely elevated left ventricular pressure into a non-compliant systemic vasculature leads to generalized endothelial cell activation, 2) the exposure of the pro-thrombotic and neo-antigenic contents of a degenerated aortic valve (known to histologically resemble atherosclerosis), and 3) the exposure of the replacement valve (bovine valve, stainless steel frame, polyester wrap). We propose that these proximate events lead to platelet activation. Given the important link between thrombosis and inflammation governed by platelet-derived mediators and leukocyte-platelet interactions, we further hypothesize that monocyte activation is mediated, at least in part, by platelet-monocyte interactions, which has been shown to induce the expansion of inflammatory monocytes⁵. Given the pro-thrombotic nature of inflammatory monocytes, we suspect a positive feedback loop may exist via the interplay of these thrombotic –inflammatory mechanisms, which may be abrogated via high potency ADP-receptor blockade (Figure 1).

If our study results indicate an improved thrombotic and immune convalescence with Ticagrelor, we would conclude that the mechanism of inflammation after TAVR is mediated in

part by platelet activation regulated by the P2Y12 receptor. This would form the basis for additional study of the clinical effects of P2Y12 blockade post TAVR, powered for clinical events. Importantly, the findings of this study might also provide mechanistic proof of principle for additional study of P2Y12 blockade in other disorders that carry elevated CV risk in the setting of chronic immune activation. One such population is the vast majority of HIV patients, who achieve controlled viremia but are left with chronic immune activation and elevated CV risk⁶.

Study Drug Background: Ticagrelor

FDA Label: https://www.accessdata.fda.gov/drugsatfda_docs/label/2015/022433s015lbl.pdf

Ticagrelor is approved by the United States Federal Drug Administration (FDA) to reduce the rate of cardiovascular death, myocardial infarction, and stroke in patients with acute coronary syndrome or a history of myocardial infarction. Ticagrelor was studied in the PLATO trial which included patients with acute coronary syndrome, randomized to Ticagrelor or Clopidogrel for 12 months. At 12 months, a composite of death from vascular causes, myocardial infarction, or stroke (the primary endpoint) had occurred in 9.8% of patients receiving ticagrelor as compared with 11.7% of those receiving clopidogrel (hazard ratio, 0.84; 95% confidence interval [CI], 0.77 to 0.92; $P<0.001$). No significant difference in the rates of major bleeding was found between the ticagrelor and clopidogrel groups (11.6% and 11.2%, respectively; $P=0.43$), but ticagrelor was associated with a higher rate of major bleeding not related to coronary-artery bypass grafting (4.5% vs. 3.8%, $P=0.03$), including more instances of fatal intracranial bleeding and fewer of fatal bleeding of other types.

4. Study objectives

Transcatheter aortic valve replacement (TAVR) has been associated with reductions in CV morbidity and death in extreme risk/surgery inadvisable patients, but cardiovascular events rates remain unacceptably high, with mortality rates of 30% and 50% at 1 and 2 years, respectively^{1,7}. Thus, even after successful treatment of aortic stenosis, this population persists with a risk of CV mortality that is 5-fold greater than cohorts studied in contemporary myocardial infarction trials such as PLATO⁸.

The mechanisms and predictors of adverse outcomes following TAVR are poorly understood. Among the most important predictor of poor outcomes is peri-procedural stroke, which is associated with a hazard ratio of 3.5 for mortality at 30 days⁹. Since 45% of cerebro-vascular accidents (CVA) occur beyond 24 hours post procedure¹⁰, optimizing anti-thrombotic therapies in the immediate post-procedure period may be a feasible strategy to reduce CVA following TAVR. However, the majority of major adverse cardiovascular events (MACE) following TAVR remains unexplained and thus, a better understanding of the mediators of CV risk is urgently needed in this high risk population. The role of anti-platelet therapy in this patient population is also uncertain. While dual anti-platelet therapy with aspirin and clopidogrel is typically recommended for a period of 6 months, its effectiveness in the prevention of adverse outcomes post-TAVR is unknown¹¹.

In patients with cardiovascular disease, among the strongest and most consistent surrogates of poor long term outcome is clopidogrel non-responsiveness. This is typically identified in 20-30% of patients with acute coronary syndromes (ACS) and is associated with an increased risk of MACE¹²⁻¹⁵. Although the prevalence of clopidogrel non-responsiveness in patients with aortic stenosis has not been previously reported, preliminary data from our group indicates a high rate of clopidogrel hyporesponsiveness (64.3%) in our post-TAVR population.

Another marker of poor prognosis in patients with cardiovascular disease is elevated proportions of CD14+CD16+ inflammatory monocytes. In an unselected cardiac catheterization population, elevated CD14+CD16+ inflammatory monocytes were associated with a hazard ratio of 3.1 for future death, MI, or stroke⁴. Our studies have recently shown that these monocytes express high levels of tissue factor and are dynamically regulated in the setting of both HIV and ACS². Interestingly, we will now report that TAVR is associated with a robust, inflammatory response characterized by a marked expansion of CD14+CD16+ inflammatory monocytes, evident even within 24 hours of an uncomplicated procedure.

The central hypothesis of our proposal is that TAVR-induced injury of the diseased native aortic valve leads to platelet deposition and inflammatory cell activation that can be attenuated by the potent anti-platelet and/or pleiotropic effects of ticagrelor. We propose a single center, prospective randomized trial to test the following specific aims:

1. **To determine whether high-potency ADP receptor blockade reduces measures of platelet activation in patients after TAVR.**
2. **To determine whether high-potency ADP receptor blockade mitigates the pro-thrombotic inflammatory response observed after TAVR.**

The co-primary study endpoints will be 1) platelet responsiveness as measured by the VerifyNow assay (platelet reactivity units, PRU) and 2) the proportion of inflammatory monocytes by polychromatic flow cytometry 1 day after TAVR. Secondary endpoints will include other measures of thrombotic and immunologic activation.

5. Study design

This is a single center, prospective, randomized, open label trial with blinded endpoint evaluation.

5.1 Screening, entry, and randomization:

Patients will be screened for inclusion/exclusion criteria as part of their pre-TAVR clinical evaluation (See Table 1). We plan to screen 150 patients per year, of whom 100 are expected to go on to TAVR. We will continue enrollment until 60 patients are randomized. All patients will be required to sign informed consent prior to planned TAVR. The scheme for a participant's movement through the trial is shown in figure 2.

Patients will be randomized in a 1:1 fashion (n=60) to either continue Clopidogrel (300mg load, 75mg daily) or begin Ticagrelor. Patients will receive a 180mg load followed by 90mg twice daily for one month. This will be an open label design given the different frequency of dosing. Decisions regarding the discontinuance of dual anti-platelet therapy after randomization will be at the discretion of the treating physician.

Patients will be seen at 30 days post TAVR per routine clinical practice. At this time, the final blood draw will be obtained. The occurrence of MACE and bleeding events will be determined by history and corroborated by examining relevant medical records. Patients will revert to clopidogrel therapy at this time and the duration of dual anti-platelet therapy will be left to the discretion of the treating physician.

5.2 Blood Biomarker Procurement:

Patients will receive a baseline blood draw prior to TAVR. Patients will then have blood draws at 24 hours, 7 days, and 30 days post procedure. Patients will be seen in followup according routine clinical practice at 7 and 30 days. All blood samples will be obtained using a 30 mL syringe which is then transferred into tubes containing 3.2% sodium citrate (blue top) or K2-EDTA (purple top). Aliquots of whole blood will be used for platelet responsiveness studies, monocyte flow cytometry, leukocyte-platelet interaction, and T cell activation studies. Plasma and Peripheral blood mononuclear cells (PBMC) will be cryopreserved at -80 and -150 degrees, respectively. Plasma based assays will be batched and performed at intervals using freshly thawed cryopreserved samples.

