using an independent samples t-test (or non-parametric test as appropriate), with significance declared for p-values <0.025 . The primary inflammatory endpoint is the percentage of inflammatory monocytes (compared to total monocytes) as a continuous variable 1 day after TAVR. The percentage of inflammatory monocytes in the Clopidogrel and Ticagrelor groups will be compared using an independent samples t-test (or non-parametric test as appropriate), with significance declared for p-values <0.025 . The percentage of inflammatory monocytes will also be compared over multiple time points to determine the trajectory and duration of the immune response, to guide duration of treatment in future studies. The values at baseline, 1 day, and 7 day will be compared within group using exploratory longitudinal mixed models to determine the kinetics of convalescence and between groups to establish whether treatment effects exist. Models that include the 30-day values also will be fit. Time period will be considered both as a continuous covariate (in days), as well as a categorical variable. Inferential interest will focus on treatment by time interaction. These models will also be used to explore the relationship between the level of P2Y12 inhibition and the reduction in inflammatory monocytes between treatments. This relationship could be different given that Ticagrelor is not only a more potent P2Y12 antagonist as compared with clopidogrel but may also have a unique dual mode of action; P2Y12 antagonism complemented with adenosine uptake inhibition.

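### The plan would credit P2Y12-regulated platelet activation if ticagrelor does better, but a two-arm comparison with clopidogrel cannot separate that route from the other ticagrelor actions the plan names

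*Combined protocol and SAP*

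**What the plan says.** All references are to the combined protocol and SAP.

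- **Planned conclusion (section 3, end of the Hypothesis text).** If thrombotic and immune recovery is better on ticagrelor, "we would conclude that the mechanism of inflammation after TAVR is mediated in" "part by platelet activation regulated by the P2Y12 receptor". The next sentence gives the use: "This would form the basis for additional study of the clinical effects of P2Y12 blockade post TAVR, powered for clinical events". The text adds that the findings might support P2Y12 work in other conditions with chronic immune activation, such as HIV.
- **Central hypothesis (section 4).** The response to valve injury can be "attenuated by the potent anti-platelet and/or pleiotropic effects of ticagrelor".
- **Aim 2 (sections 2 and 4).** "To determine whether high-potency ADP receptor blockade mitigates the pro-thrombotic inflammatory response observed after TAVR".
- **Statistical plan (section 5.3).** Each co-primary endpoint, day-1 PRU and day-1 percentage of inflammatory monocytes, is compared between arms by a t-test or a non-parametric alternative. Exploratory longitudinal mixed models will also be used to "explore the relationship between the level of P2Y12 inhibition and the reduction in inflammatory monocytes between treatments". The plan says this relationship could differ because ticagrelor "may also have a unique dual mode of action; P2Y12 antagonism complemented with adenosine uptake inhibition".
- **Other mechanism measures.** Section 5.3 lists secondary thrombotic and immune markers and treats them as essential for working out mechanism. Section 5.5.c defines the monocyte-platelet aggregate measures.

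**The concern.** Section 3 sets out an if-then inference. The condition is a better result on one drug than on another. The conclusion is about one receptor pathway. Elsewhere the same document says that the drug may work through that pathway, through something else, or through both. A reader following section 3 as written would therefore attribute the effect to P2Y12 without the design having shown it.

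The trial is titled mechanistic, so this interpretation is a main product of the study. Section 3 would use it to justify a larger outcome trial of P2Y12 blockade after TAVR and possibly work in other diseases. If the monocyte effect came from another action of ticagrelor, the planned wording would still point that later work at P2Y12 blockade as a class.

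**Working it through.** **1. The plan's own figure.** Section 5.6 gives a 4-point difference, SD 5, 30 per arm, two-sided alpha 0.025 and 80% power.

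- Standardised difference: 4/5 = 0.8.
- Normal approximation: 0.8 × √(30/2) = 0.8 × 3.873 = 3.098. Subtracting the critical value 2.241 leaves 0.857, and Φ(0.857) = 0.804.
- Noncentral t: 0.785.

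Both agree with the stated 80% to within 2 points. The sample size is not in question.

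**2. What the contrast estimates.** Write the monocyte difference between arms as

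total effect = part through P2Y12 + part through other actions.

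The arms are ticagrelor and clopidogrel, both on background aspirin. No arm gives stronger P2Y12 blockade without ticagrelor's other possible actions, and no arm gives those actions without stronger P2Y12 blockade. The data therefore supply one equation with two unknowns. With the planned total of −4 points:

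| Through P2Y12 | Through other actions | Total |
|---|---|---|
| −4 | 0 | −4 |
| −2 | −2 | −4 |
| 0 | −4 | −4 |

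The expected between-arm difference is the same in all three rows. At a fixed total and SD, so is the chance of a significant monocyte test. In the third row the words in part are false, since they assert a P2Y12 share above zero.

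**3. What lower PRU adds.** A fall in PRU would show stronger P2Y12 inhibition on ticagrelor, which is aim 1. It would not show that this inhibition caused the monocyte change. In the third row PRU falls, monocytes fall, and the two are linked only through the drug.

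**4. What the exploratory model adds.** The section 5.3 model relating P2Y12 inhibition to monocyte reduction is the planned analysis closest to the question. Treatment is randomised, but PRU is measured after randomisation and is not randomised within an arm. A patient characteristic that affects both PRU and monocytes would produce an association without a causal P2Y12 route. Patients also enter with differing P2Y12 exposure (sections 2 and 5.11), so within-arm PRU partly reflects history. That history would confound only if it also marked something related to monocytes. The documents give no mediation method or assumptions for this analysis.

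**5. Whether the conclusion waits for that model.** Section 3 refers to neither the model nor the aggregate measures. Sections 5.3 and 5.5.c do not say that a P2Y12 attribution requires a particular result from them.

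**The case against.** The strongest reply is that the plan already handles this. It discloses the alternative routes itself, schedules a model on the PRU-monocyte relationship, and calls the secondary measures essential to mechanism. Section 3 is hedged throughout, cites earlier evidence that platelet-monocyte interaction expands inflammatory monocytes, and leads only to further study. It speaks of convalescence, a word section 5.3 uses for the longitudinal models, so its condition may cover the whole body of results and not just the day-1 tests.

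Much of this stands. The plan does not overlook other mechanisms, and the wider reading of convalescence is reasonable. What does not follow is that the conclusion is protected. On the wider reading the treatment-by-time comparisons still contrast the two drugs, and nothing requires the PRU-monocyte analysis to support P2Y12 before the conclusion is drawn. Earlier evidence makes the route plausible; it does not make this contrast identify it.

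A reader might infer three stronger points that the documents do not support:

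- **That ticagrelor is shown to act by another route.** Section 5.3 says only that it may, and section 4 says and/or. These are possibilities.
- **That the roughly 80% power is a rate of false attribution.** It is the ordinary power for the total effect and cannot depend on route.
- **That the exploratory model would mislead in some stated share of trials.** Any such share needs a within-arm PRU-monocyte correlation from a shared cause, which the documents do not give, and would have to be worked out for the longitudinal models actually planned.

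**Conclusion.** The concern holds in a limited form. As written, section 3 draws a P2Y12-specific conclusion from a result that shows only a drug effect, while sections 4 and 5.3 name possible alternatives that the design cannot separate. Aim 2 uses the same terms, although there high-potency ADP receptor blockade may be no more than a label for the ticagrelor arm.

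No numerical size attaches to the point. It rests on the two-arm design and the plan's own statements about ticagrelor, not on any assumed correlation or effect split. Severity is low: no endpoint, test, alpha level or decision rule is wrong, and the exploratory mechanism work is worth doing. What changes is the claim the trial can make.

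**What to change.** 1. **Reword the conclusion in section 3**, for example: *A positive result would show that ticagrelor, compared with clopidogrel, lowers PRU and/or the percentage of inflammatory monocytes after TAVR. This would be consistent with P2Y12 blockade and/or other actions of ticagrelor.*
2. **Read aim 2 (sections 2 and 4) in the same way**, as a question about ticagrelor compared with clopidogrel.
3. **Add a sentence to section 5.3** stating that any attribution to P2Y12 is exploratory; that it rests on the PRU-monocyte models and secondary markers of section 5.3 and the monocyte-platelet measures of section 5.5.c; and that it may be confounded because PRU is measured after randomisation and is not randomised within arm.

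No particular covariate set is needed for this. The cost is a few sentences and a more modest mechanistic claim. Data collection, sample size, alpha and the primary tests do not change.
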